6.1 Inclusion Criteria

- a. HCW using PPE at least 6 hours/day, 4 days/week or, depending on shift work, 24 hours/week, for at least one (1) month
- b. Men or women, any age
- c. Overall skin irritation score of at least 4 on 0-10 scale where 0 = none and 10 = worst
- d. Willing to stop use of any other emollient and lotion for one (1) week between screening and baseline visit and for the duration of the study.
- e. Participant is willing to stop use of or not begin use of any topical corticosteroids, emollients and lotions to the hands and face for the duration of the trial.

6.2 Exclusion Criteria

a. History of any skin disorder existing prior to March 1, 2020 characterized by chronic visible lesions or skin irritation symptoms including, but not limited to

atopic dermatitis, eczema, moderate-severe acne, chronic dry skin and psoriasis.

- b. Use of topical corticosteroids within one (1) month of baseline visit.
- c. History of any significant medical condition that, in the opinion of the investigator, might put the subject at risk in this trial.
- d. Participation in another clinical trial within 30 days or 5 half-lives of the study agent, whichever is longer.

7. Test Item and Proscribed Treatments

This is an open label study. All subjects will receive EpiCeram, delivered in 90 gm tubes. The EpiCeram cream will be applied to face and hands at least three (3) times per day, about every 8 hours taking care to apply after bathing and before applying any makeup. Subjects are prohibited from using any other skin lotion by prescription or over the counter. Subjects are specifically prohibited from using any corticosteroid containing skin products.

8. Number of Subjects

Fifty (50) subjects will be evaluated in this study. To account for subjects who fail to complete the trial fifty-five (55) subject will be enrolled.

9. Safety measurements Adverse events

10. Efficacy measurements

- a. Symptom scales
- b. TEWL
- c. Hydration
- d. Skin pH
- e. Skin surface bacterial qPCR

11. Study Procedures

11.1 Screening visit

At least one (1) week prior to the baseline visit patients will be evaluated for inclusion in the study. Patients will have the study thoroughly explained to them and all their questions will be answered. Patients will sign the Informed Consent Document (ICD) before any study related procedures are performed. By definition, a patient becomes a study subject once he/she has signed the informed consent document. Every patient must have the opportunity to take home an unsigned copy of the ICD to discuss the study with family or friends and consider their decision whether to participate.

Screening and Baseline procedures may occur on the same day the study is first presented if the patient elects to proceed at that time and meets the inclusion and exclusion criteria including the washout requirement. A manual describing detailed steps for collection of laboratory, photographic and skin surface measurements will be provided to the site by the sponsor. At the Screening visit, each subject will be entered into the EDC system using a DDC tablet which will issue a unique identifier.

Subjects who agree to participate will perform the following:

- a. Review and sign the Informed Consent Document including consent for photos.
- b. Assess for overall irritation score of ≥ 4 on the previously described scale of 0-10.
- c. Assess for meeting all inclusion and exclusion criteria.
- d. The subject will be instructed to stop using (washout) emollients and lotions currently in use on the hands and face for one (1) week and for the duration of the study.
- e. The subject will be instructed to return in one (1) week for the Baseline visit. If washout requirement is met, Baseline visit activities may be performed at the Screening visit. Instruct subjects to refrain from washing hands and face for 2-hours prior to each visit.

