This will be a one (1) month, open label study. Subjects must be HCW who have used face and hand PPE at least four (4) days a week for a minimum of one (1) month (or, depending on shift work, at least 24 hours/week) and who have new (after March 1, 2020) symptomatic skin irritation on the hands and/or face. No change to required hand washing protocols or other protective measures will be required.

At Visit 1 (Screening) the study will be explained, and an informed consent document (ICD) signed. Subjects will be entered into the electronic data capture (EDC) system using a direct data capture (DDC) tablet. Subjects will complete an overall skin irritation assessment on 0-10 scale where 0 = none and 10 = worst. If it is equal to or greater than 4, the subject may proceed to enrollment provided all other inclusion and exclusion are met.

If the subject has not used any lotions and emollients for the previous one (1) week on the face and hands, washout is not necessary, and Baseline visit activities may be performed at the Screening visit. Subjects requiring washout, will refrain from using any lotions and emollients for one (1) week between Visits 1 and 2 and then, for the duration of the study. Visit 2 (Baseline) will occur seven (7) days after Visit 1.

At Visit 2, subjects will complete an overall skin irritation assessment on a 0-10 scale where 0 = none and 10 = worst. Subjects will complete skin symptom scales of pain, redness, dryness, roughness, itching and cracking on a scale on a 0-10 scale where 0 = none and 10 = worst. A manual describing detailed steps for collection of laboratory, photographic and skin surface measurements will be provided to the site by the sponsor. Vendors will supply training and references for the camera and EDC system.

Photographs: Digital 3D photographs will be taken of the face and back of the hand. The face photo will be a two (2) inch by three (3) inch area of the cheek without identifying features. The hand photo will be the worst area of involvement as selected by the subject. Skin Function Testing: Measurements of transepidermal water loss (TEWL) with stratum

corneum hydration (SCH) and surface skin pH will be taken on the web between the 3rd and 4th metacarpophalangeal (MCP) joints on the dorsum of the dominant hand used.

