Descriptive statistics will be calculated for all demographic and clinical characteristics at baseline and study outcomes for each time period. Means and standard deviations will be presented for continuous variables (e.g., age) and proportions and frequencies for categorical

variables (e.g., sex). Paired t-tests will be used to assess unadjusted differences in primary outcomes of face and hand skin irritation symptoms (pain, redness, dryness, cracking, roughness, itching and overall skin irritation) and secondary outcomes of pH, TEWL, and S. aureus colonization level between the baseline visit and Day 28 follow-up visit. Analysis will be performed on the Intention-to-Treat (ITT) sample. Standard data quality checks will be performed. The sample size of n = 50 is sufficiently powered $(1 - \beta = 0.80)$ to identify a medium effect size of d = 0.4 in a two-tailed test with α set at 0.05. Given the multiple primary endpoints, *p*-values will be reported with high precision (four percentage points) to allow for multiple comparisons adjustments as desired.

EpiCeram for skin protection in healthcare workers using personal protective equipment.

Protocol #: PPE-01

1. Introduction:

During the current COVID-19 pandemic, health care workers (HCW) report that the prolonged use of personal protective equipment (PPE), particularly gloves and face covering, results in irritant contact dermatitis manifested by symptoms of pain, itching, burning and non-specific discomfort of the hands and face and associated visible physical changes of erythema, dryness, roughening and cracking of the affected skin (Jiang, et al 2020). These changes are aggravated by frequent hand washing and antimicrobial alcohol use. These irritative changes are likely associated with defects in the normal barrier structure and function of the skin, including, but not limited to, lowering of pH, excessive water loss, alteration of skin microbiome, lowered resistance to allergens and pathogens and immunological dysfunction. It is unknown whether these changes could increase the likelihood of S. aureus skin contamination or, in people exposed to, but not systemically ill with, COVID-19 to act as "silent" carriers of coronavirus.

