11.2 Baseline Visit

Perform photos, skin function testing and laboratory testing in the order listed below.

- a. Assess for overall irritation score of ≥ 4 on the previously described scale of 0-10.
- b. Assess for adverse events and changes to skin routine.
- c. Complete skin symptom rating scales.
- d. Take digital photos of hand and face.
- e. Measure skin surface TEWL and SCH.
- f. Measure face and hand skin surface pH.
- g. Swab the dominant hand for bacterial qPCR.
- h. Perform tape stripping for free fatty acids and AMPs.
- i. Dispense one unit of EpiCeram.
- j. Subject will apply EpiCeram TID at home to clean face and hands (wrist to fingertips, back and front).

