Appendix II

Schedule of Events

VISIT	V1	V2	V3
WEEK	Screen	Baseline**	DAY 28**
Window	-7 d	+/- 2d	+/- 2d
Informed Consent/Photo Consent	x		
Inclusion/Exclusion	x		
Demographics	x		
Current Face & Hand Treatment	X		
Medical History of Skin Disease	x		
Overall symptom rating	X	X	X
Skin symptoms rating		X	X
Photos of face and hand*		X	X
TEWL and SCH face and hand*		X	X
Skin pH face and hand*		X	X
Swab of dominant hand*		X	X
Tape Strip dominant hand*		X	X
Subject Response per Pl			X
Dispense Product		X	
Collect Product			X
Adverse Events		X	X
Changes to skin care		X	X

* Perform in the order listed. ** Instruct subject to stop washing hands and face for 2-hours prior to visit.

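### Same-day Baseline can bypass the protocol's own 2-hour no-wash rule, so TEWL, pH and the S. aureus swab may be taken under different conditions at Baseline and Day 28

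*Combined protocol and SAP*

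**What the plan says.** **The rule.** Section 11.1, item e, under the Screening visit: "Instruct subjects to refrain from washing hands and face for 2-hours prior to each visit". The footnote to the Schedule of Events in Appendix II repeats it: "Instruct subject to stop washing hands and face for 2-hours prior to visit". The footnote mark stands on the Baseline and Day 28 columns and not on the Screen column.

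**The same-day route.** The Synopsis (Study design) has the study explained for the first time at Visit 1: "At Visit 1 (Screening) the study will be explained, and an informed consent document (ICD) signed". Section 11.1 then says "Screening and Baseline procedures may occur on the same day the study is first presented if the patient elects to proceed at that time", provided that the selection criteria and the washout requirement are met. Item e adds: "If washout requirement is met, Baseline visit activities may be performed at the Screening visit". The Synopsis and Section 3 give the same permission to anyone who has used no lotion or emollient on the face and hands for a week: "washout is not necessary, and Baseline visit activities may be performed at the Screening visit".

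**The measurements.** Sections 11.2 and 11.3 list TEWL with SCH, pH ("Measure face and hand skin surface pH"), the dominant-hand swab and the tape strips at both Baseline and the Final Visit. Both lists ask about changes to skin routine. Neither asks when the subject last washed, and neither sets a waiting period.

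**The analysis.** Section 21.0 compares Baseline with Day 28 by paired t-test for pH, TEWL and S. aureus colonization level. All subjects receive EpiCeram (Section 7).

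**The concern.** The sponsor chose to standardise time since washing before skin measurements, and the Background gives a reason to care about washing: "These changes are aggravated by frequent hand washing and antimicrobial alcohol use". A subject whose first contact with the study is the Screening visit, and who goes on to Baseline that day, receives the instruction too late for it to cover the preceding 2 hours. By Day 28 the same subject has had the instruction. The two ends of the paired difference can therefore be measured under different conditions.

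With no control arm, any systematic difference between visits goes straight into the mean change. If recent washing raised TEWL or pH at Baseline, part of an apparent fall would be an artefact. If it removed bacteria from the palm, a real fall in S. aureus would be hidden or a false rise would appear. These are conditional statements, because the documents do not say what washing does to the readings within 2 hours. The three secondary endpoints, and with them objectives 2 and 3, are exposed. The primary symptom scores are subject ratings and are less directly exposed.

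**Working it through.** **1. Order of procedures for a same-day subject**

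| Step | Source | Does it secure 2 wash-free hours? |
|---|---|---|
| Study explained, consent signed | Synopsis; Section 3; Section 11.1 | No |
| Eligibility and emollient washout checked | Section 11.1, items b to e | No; washing is not a condition |
| No-wash instruction given | Section 11.1, item e | Only for later visits |
| Baseline ratings, photographs, TEWL/SCH, pH, swab, tape strips | Section 11.2 | No check, wait or time field |
| Day 28 measurements | Section 11.3; Appendix II | Instruction has been given; compliance is not recorded |

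The gap follows from this order alone and needs no arithmetic.

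**2. The plan's own sample size**

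Inputs from the Synopsis (Statistics): d = 0.4, two-sided alpha 0.05, power 0.80, n = 50. The paired formula is n = ((z for 0.975 + z for 0.80) / d)² = ((1.960 + 0.842) / 0.4)² = 49.1, so 50. Power at n = 50 is 0.807 by the normal approximation and 0.792 by the exact noncentral t, which needs 52. The stated figure reproduces, and the present point does not change it.

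**3. How large the bias could be**

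Let f be the share of subjects who both have same-day Baseline and washed within 2 hours. Let s be the shift that recent washing causes in the Baseline reading, in SDs of the paired change. Then

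bias in the mean change = f × s.

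The documents give neither f nor s, so both are assumptions. At f = 50% and s = 0.5 the bias is 0.25 SD, and 0.25 / 0.4 = 63% of the design effect. At f = 10% and s = 0.25 it is 0.025 SD, and 0.025 / 0.4 = 6%.

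In a simulation (40,000 runs per cell, n = 50, SD of change 1, no product effect), f × 50 subjects were shifted by s and the two-sided 0.05 paired t-test applied. Rejection rates, against a nominal 0.05:

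| Share affected | s = 0.25 | s = 0.5 | s = 1 |
|---|---|---|---|
| 10% (5 of 50) | 0.052 | 0.061 | 0.090 |
| 25% (12 of 50) | 0.067 | 0.126 | 0.316 |
| 50% (25 of 50) | 0.134 | 0.385 | 0.899 |
| 75% (38 of 50) | 0.253 | 0.739 | 0.999 |

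The effect is negligible in the top left of the table and severe in the bottom right. The documents do not show which cell applies, and as written the trial would not collect the data to find out.

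**The case against.** The strongest reply is that the rule is not waived for same-day subjects. Section 11.1 applies it before each visit, and the Appendix II footnote sits on the Baseline column with no exception. Same-day Baseline is optional: a site could give notice when booking, keep the subject for 2 hours, or schedule Visit 2. Subjects may also take the consent document home before deciding. This stands in part. The rule exists; what is missing is a step that makes it operate on the same-day route.

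A second reply is that the sponsor's procedures manual, cited in the Synopsis and in Sections 3 and 11.1, may set pre-measurement conditions. That is possible and could not be checked. If it does, the protocol need only refer to it.

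Third, consent, data entry, eligibility review, symptom scales and photographs all come before TEWL, and the swab comes later still. This shortens the shortfall, but nothing shows that it fills 2 hours.

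Four stronger readings are tempting, and the documents support none of them:

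- **No same-day subject could have been told.** This is true only of the steps that the protocol describes; advance notice is not ruled out.
- **Every same-day subject is affected.** Only those who washed within 2 hours are.
- **The bias favours EpiCeram.** The Background says that frequent washing aggravates the skin changes. It does not give an acute effect on TEWL, pH or qPCR, and the direction could differ by endpoint.
- **The silence on alcohol sanitiser is part of the same defect.** The rule omits sanitiser at Baseline and Day 28 alike, so the omission does not create this asymmetry. Extending the rule to sanitiser is a separate preference.

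**Conclusion.** The point holds as a procedural gap. Following the protocol as written, a site can take Baseline skin measurements and the swab without the 2-hour interval that the protocol itself calls for, whereas by Day 28 every subject has had the instruction. In a single-arm paired analysis this can bias the changes in TEWL, pH and S. aureus.

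The size is unknown. It rests on two quantities absent from the documents: the share of subjects with same-day Baseline who washed within 2 hours, and the shift that such washing causes. Over assumed shifts of 0.25 to 1 SD, false rejection runs from about nominal (0.05 to 0.09) if 10% are affected to 0.13 to 0.90 if 50% are. No single value in that range should be quoted as the expected bias.

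Confidence is high for the sequence of steps in the protocol text and limited for the practical effect, since the manual was not seen. The change should be made before enrolment, because time of last wash cannot be recovered reliably afterwards.

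**What to change.** 1. In Sections 3 and 11.1 and in Appendix II, allow same-day Baseline skin measurements and swab only if the subject confirms no hand or face washing in the previous 2 hours. Otherwise the subject waits on site until 2 hours have passed or returns for Visit 2. Carry the same condition into the Synopsis.
2. Add to Sections 11.2 and 11.3, and to the data collection tool, the time of last hand and face wash at Baseline and Day 28. Time of last sanitiser use is an optional further field.
3. In Section 21.0, add a sensitivity analysis of TEWL, pH and S. aureus that excludes subjects who did not meet the 2-hour condition at both visits.
4. If the procedures manual already sets this condition, cite it at each of these places.

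**Cost.** Short edits in several sections, one or two time fields per visit, and one repeat of three paired analyses. Some same-day subjects wait up to 2 hours or make a separate visit. The sample size does not change.

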11.2 Baseline Visit

Perform photos, skin function testing and laboratory testing in the order listed below.

- a. Assess for overall irritation score of ≥ 4 on the previously described scale of 0-10.
- b. Assess for adverse events and changes to skin routine.
- c. Complete skin symptom rating scales.
- d. Take digital photos of hand and face.
- e. Measure skin surface TEWL and SCH.
- f. Measure face and hand skin surface pH.
- g. Swab the dominant hand for bacterial qPCR.
- h. Perform tape stripping for free fatty acids and AMPs.
- i. Dispense one unit of EpiCeram.
- j. Subject will apply EpiCeram TID at home to clean face and hands (wrist to fingertips, back and front).

11.3 Final Visit (4 weeks)

Perform photos, skin function testing and laboratory testing in the order listed below.

- a. Assess for overall irritation score of ≥ 4 on the previously described scale of 0-10.
- b. Assess for adverse events and changes to skin routine.
- c. Complete skin symptom rating scales.
- d. Take digital photos of hand and face.
- e. Measure skin surface TEWL and SCH.
- f. Measure face and hand skin surface pH.
- g. Swab the dominant hand for bacterial qPCR.
- h. Perform tape stripping for free fatty acids and AMPs.
- i. Investigator assessment of subject's Response to Therapy on a 1-5 scale, with 1 = no response and 5 = best response.
- j. Resolve AEs.

12.0 Study Withdrawal

Subjects may be withdrawn from the study for one or more of the following reasons.

- a. Request for withdrawal by the subject for any reason whether or not related to an AE.
- b. Lost to follow-up.
- c. Noncompliance with the protocol.
- d. Unacceptable adverse event. In this case the decision to remove the subject from the study may be made by the subject, the investigator or Primus.
- e. Determination by the investigator or Primus, that, withdrawing from the study is in the best medical interest of the subject.
- f. Administrative reasons such as early termination of the study.
- g. Treatment failure requiring an increase or addition of concomitant medication (s) or the use of any excluded medication.
- h. If the subject is discontinued prior to receiving the first dose of study product AEs and SAEs will be collected until the termination visit. If the subject has received study medication AEs and SAEs will be collected until the termination visit or until 30 days after the last dose of study product, whichever is later All AEs and SAEs must be followed until resolution or stability.

According to FDA and the Declaration of Helsinki a subject in a clinical trial has the right to withdraw at any time and for any reason without prejudicing his/her future medical care at the investigative site. In the case of early withdrawal of a subject, the investigator should make all reasonable efforts to have the subject attend a termination visit and document all details of the early termination on the appropriate data collection tool/CRF.

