13.0 Early Termination Visit Procedures

If a subject wishes to end his/her participation in the study prematurely, whether because of an AE or any other reason, he/she should be asked to complete a termination visit at the next scheduled appointment or within 14 days, whichever is more convenient. The investigator should make every reasonable attempt to perform the final assessment. Whenever possible, all final visit procedures should be performed at the time of an early termination visit. All outstanding AEs should be followed to resolution or stability. The reason for early termination should be clearly stated in the source and data collection tool.

All adverse events that result in a subject's withdrawal from the study must be reported to the Project Manager of Clinical Investigation, [name], BSN [contact] cell), within 24 hours.

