21.0 Statistical considerations

Descriptive statistics will be calculated for all demographic and clinical characteristics at baseline and study outcomes for each time period. Means and standard deviations will be

presented for continuous variables (e.g. age) or proportions and frequencies for categorical variables (e.g., sex) to describe the sample.

Paired t-tests will be used to assess differences in the primary outcomes of face and hand skin irritation symptoms (pain, redness, dryness, cracking, roughness, itching and overall skin irritation) between the baseline visit and Day 28 follow-up visit. The same analysis will be conducted for the secondary outcomes of pH, TEWL, and S. aureus colonization level. All statistical tests for the primary outcomes will be conducted will be two-tailed with α set at 0.05. All *p*-values will be reported with high precision (to the 4th decimal place) so that multiple comparisons adjustments may be applied, as desired. Table 1 below shows how the results will be presented.

The analysis will be performed on the Intention-to-Treat sample. If there is attrition over the course of the study, attritors will be compared to completers in terms of measures taken at baseline. Any significant differences will be reported.

All variables will be checked for outliers and skewness by visually examining boxplots. Further evaluation of any outliers identified through visual checks will be conducted to assess if any participants should be excluded from the analysis. The assumptions for each inferential statistical test will be evaluated. In the event assumptions are not met, results from a Wilcoxon signed rank test will also be reported.

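### Subjects withdrawn for treatment failure may be missing from the Day 28 test or be scored after added treatment, and the undefined ITT sample does not say how they count

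*Combined protocol and SAP*

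**What the plan says.** **Withdrawal (Section 12.0).** The list of grounds opens permissively: "Subjects may be withdrawn from the study for one or more of the following reasons". Item (g) is "Treatment failure requiring an increase or addition of concomitant medication (s) or the use of any excluded medication". Item (c) is noncompliance with the protocol. The section also asks the investigator to make reasonable efforts to bring a withdrawn subject to a termination visit.

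**Termination visit (Section 13.0).** The subject is asked to "complete a termination visit at the next scheduled appointment or within 14 days, whichever is more convenient". On content: "Whenever possible, all final visit procedures should be performed at the time of an early termination visit". The reason for stopping early must be recorded.

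**Visits (Appendix II).** Visit 3, at Day 28, is the only scheduled visit after baseline. Changes to skin care are collected there (also Section 11.3, item b).

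**Analysis (Section 21.0).** "Paired t-tests will be used to assess differences in the primary outcomes of face and hand skin irritation symptoms", comparing the baseline and Day 28 visits. "The analysis will be performed on the Intention-to-Treat sample". If there is attrition, "attritors will be compared to completers in terms of measures taken at baseline". The section does not define the ITT sample. It does not say whether a termination-visit score stands in for Day 28, what happens when the Day 28 score is missing, or how a score obtained after added treatment is handled.

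**Endpoints and size.** Section 4 words both primary endpoints as changes of at least 2 points on a 0–10 scale. Section 8 says: "To account for subjects who fail to complete the trial fifty-five (55) subject will be enrolled"; 50 are to be evaluated. All subjects receive EpiCeram (Section 7).

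**The concern.** A paired test can use only subjects with two scores. Section 12.0(g) provides a way out of the study for the subjects in whom EpiCeram has not been enough, and nothing in Sections 12.0 or 13.0 keeps them under assessment until Day 28. The ITT label does not bring them back, because the plan supplies no rule for a missing second score.

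The termination visit only partly helps. After baseline, the next scheduled appointment is Visit 3 itself, so the visit can fall well after other treatment has started. If that score is used, any benefit of the other treatment is counted as change on EpiCeram.

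This matters more in a one-arm before-after study than in a controlled one. There is no comparison group to lose failures at a similar rate, so selective loss moves the estimate itself. The planned attrition check cannot reveal it, because failure happens after baseline and the check looks only at baseline values. How failures count would be decided after the data are seen, on seven symptom scales and on the two-point endpoints.

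**Working it through.** **1. The plan's own figure.** Inputs (Synopsis, Statistics and Number Subjects): n = 50, d = 0.4, two-sided α = 0.05, power 0.80, 55 enrolled. A paired t-test with these inputs has power 0.792 (noncentral t) or 0.807 (normal approximation), which agrees with 0.80. The sample size calculation is not in dispute. Planned losses are 55 − 50 = 5.

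**2. What can happen to a subject who meets 12.0(g).** Reading Sections 12.0, 13.0 and 21.0 together gives four routes:

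- Withdrawn, no termination visit: no second score, so absent from the paired test. The mean shifts in EpiCeram's favour if such subjects did worse than completers.
- Withdrawn, scored after added treatment, score used as Day 28: EpiCeram is overstated if the added treatment helped.
- Not withdrawn (the wording is permissive), scored at Visit 3 after added treatment: same effect.
- Withdrawn, scored before added treatment starts or acts, score used as Day 28: the failure is recorded and nothing is overstated.

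The plan does not say which applies.

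**3. Illustration on the 0–10 scale.** Assumptions, none of them in the documents: 50 completers with mean change −2.0, of whom 60% (30) improve by at least 2 points; all 5 planned losses are failures.

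All-enrolled mean = (50 × completer mean + 5 × failure mean) / 55

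- Failures unchanged: (50 × −2.0 + 5 × 0) / 55 = −100/55 = −1.82
- Failures worse by 2: (50 × −2.0 + 5 × 2) / 55 = −90/55 = −1.64
- Improved share, failures counted as not improved: 30/55 = 54.5%, against 30/50 = 60%

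**4. Effect on the test.** Assume a completer improvement equal to the planned effect, 0.4 SD. Completers alone give t = 0.4 × √50 = 2.83, p = 0.0068. Putting back 5 failures (no spread if unchanged, SD 1 if worsened):

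| Failures' mean change | All-enrolled mean (SD units) | Reduction | p |
|---|---|---|---|
| none | (50 × 0.4 + 0)/55 = 0.364 | 9% | 0.0069 |
| worse by 0.5 SD | (20 − 2.5)/55 = 0.318 | 20% | 0.025 |
| worse by 1 SD | (20 − 5)/55 = 0.273 | 32% | 0.064 |

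**5. False-positive rate.** Simulation with a true mean change of zero, where 5 of 55 leave through a process correlated with the change score:

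| Correlation | Shift in completers' mean (SD) | Two-sided rejection rate |
|---|---|---|
| 0 | 0.00 | 5.0% |
| 0.3 | 0.05 | 6.7% |
| 0.5 | 0.09 | 10.3% |
| 0.7 | 0.12 | 16.2% |
| the five worst all leave | 0.18 | 31% |

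**The case against.** The strongest reply is that the protocol already tries to capture these subjects. Withdrawal is optional, a termination visit is actively sought with all final procedures where possible, and 14 days is an outer limit, so the visit may come before other treatment starts or works. That score, if used, would record the failure properly. This stands, and it rules out two stronger readings that a reader might infer: that every withdrawn subject drops out of the test, and that both remaining routes must overstate EpiCeram. The documents support neither. The direction is the expected one, and it depends on failures having done worse than completers or on the added treatment having helped.

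A reader might also treat withdrawal for noncompliance under 12.0(c) as treatment failure. The text does not say so: noncompliance covers any breach, including missed applications or use of another lotion out of habit. Nor does enrolling 55 to evaluate 50 show that a completer analysis is intended; inflating enrolment for dropout is ordinary and compatible with ITT.

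On size, every failure rate and outcome above is assumed. Section 12.0 lists reasons for loss unrelated to failure, so taking all 5 losses as failures is unfavourable by construction. With 5 unchanged failures the p-value hardly moves. Section 21.0 also plans no responder analysis, so the 60% versus 54.5% contrast bears on the endpoints as worded in Section 4, not on a test the plan specifies.

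What remains is that a requested visit is not an assured one, and no text says how its score, or its absence, enters the analysis.

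**Conclusion.** The point holds as a change that should be made. The plan permits failures to leave, does not assure an untreated second score, and relies on an ITT label without a definition. The expected effect in this one-arm study is some overstatement of improvement.

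The size cannot be derived from the documents. If all 5 planned losses are failures, the mean falls by about 9% when they are unchanged, with almost no effect on p. It falls by 20% to 32% when they worsened by 0.5 to 1 SD, enough at the upper end to lose nominal significance for an effect of the planned size. If losses are unrelated to outcome, there is no bias.

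**What to change.** **Sections 12.0 and 13.0.** State that withdrawal from product does not by itself end outcome assessment, that the subject is still scored at the existing Day 28 visit if willing, and that the date and type of any added treatment are recorded. Changes to skin care and the reason for early termination are already collected, so this is a small extension. When and how to treat a failing subject stays with the investigator.

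**Section 21.0.**

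- Define ITT as all enrolled subjects who received product.
- State whether a termination-visit score counts as Day 28.
- Count subjects meeting 12.0(g) as not improved on the Section 4 two-point endpoints.
- For mean change, report sensitivity analyses with failures and missing scores set to no change and to worsening, with the number of failures.
- Report use of a prohibited lotion separately, and do not automatically count it as failure.

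**Cost.** A short amendment, minor extra analysis and a slightly less favourable estimate. No new scheduled visit is needed.
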